3 SYNOPSIS

Protocol Number: RD.06.SPR.115230

Title: A double-blind, multicenter, long-term follow-up study to assess recurrence of Actinic Keratosis in subjects treated with Methyl aminolevulinate hydrochloride (MAL) 16.8% cream (CD06809-41) or vehicle cream in the treatment of thin and moderately thick, non-hyperkeratotic, non-pigmented actinic keratosis of the face and scalp when using daylight photodynamic therapy (DL-PDT), for subjects achieving complete response of treated lesions at Final Visit in Study RD.06.SPR.112199

Investigational Product: none

IND Number: CCI

Study Centers: Approximately 60 study centers are planned in the United States

Phase: 3

Objectives:

Primary objective: The primary objective of this study is to assess recurrence of lesions treated in RD.06.SPR.112199 for those subjects who achieved Complete Response (CR) of treated AK lesions. They will be offered the opportunity to participate in this 9-month long-term follow-up study (i.e., 52 weeks after the last DL-PDT), continuing the double-blind conduct of this study.

Secondary objective: The secondary objective of this study is to evaluate the long-term safety of MAL DL-PDT and vehicle cream DL-PDT for 52 weeks after the last DL-PDT for those subjects who achieved Complete Response (CR) of treated AK lesions in study RD.06.SPR.112199

Study Design: This is a double-blind, multicenter, parallel group, vehicle-controlled long-term follow-up study to evaluate recurrence of AKs in subjects who completed study RD.06.SPR.112199. Only those subjects who achieved CR of treated AK lesions at the Final Visit (12 weeks after the last DL-PDT session) will be offered the opportunity to continue to be followed in the current study for 9 months to assess recurrence. After obtaining informed consent for this follow-up study, the subjects will return at Weeks 14 and 40, which correspond to 26 and 52 weeks after the last DL-PDT session, respectively to assess the lesions treated in the previous study for recurrence of AK. Recurrence will be determined by reappearance of those lesions completely cleared by 2 DL-PDT sessions, i.e., subjects whose lesions are evaluated to be non-CR at the visits in this study will be deemed to have recurrence. If the percentage of subjects maintaining complete response would be 60% at Visit 3 (52 weeks after the last DL-PDT), 40% of subjects would have experienced recurrence (subject recurrence response). The same calculation will be done for lesion complete response, to assess the lesion recurrence. There will be a telephone check-in with the subjects by the clinical site at Week 40 to help retain the subject's participation for the entire duration of the study. CCI

Number of Subjects:

Approximately 111 subjects from the MAL cream arm and 19 subjects from the vehicle cream arm from the previous study are expected to enroll in the follow-up study.

Treatment:

Neither investigational product nor intervention will be part of this study.

Study Duration:

The expected duration for each subject's participation in the study will be approximately 40 weeks from the completion of study RD.06.SPR.112199.

Study Population:

The study population will consist of adult male and female subjects with clinically confirmed mild to moderate actinic keratosis on the face and balding scalp, who have completed study RD.06.SPR.112199 with a Complete Response at Final Visit of that study, meaning those subjects, whose treated AKs were all cleared at 12 weeks after the last DL-PDT session.

Inclusion Criteria: To be eligible for study entry, subjects must satisfy all of the following inclusion criteria:

1. Subjects who have participated in study RD.06.SPR.112199 and have achieved a complete response at the Final Visit of that study, defined as complete clearance of all treated lesions at 12 weeks after the last DL-PDT
2. Written Informed Consent before any assessment related to the LTFU study is performed
3. Willing and capable of complying with requirements of the protocol

Exclusion Criteria: Subjects will be excluded from the study if 1 or more of the following exclusion criteria are applicable:

1. Subjects, who develop or experience a condition that may compromise subject safety or compliance, interfere with evaluation or preclude completion of the study. In particular, these conditions include, but are not limited to malignancy or other life threatening diseases.
2. Pertinent non-compliance with the conditions for this study or instructions by the investigator during RD.06.SPR.112199

Primary Endpoint:

- Subject recurrence, defined as the proportion of subjects with recurrence of any (≥ 1) cleared treated AK lesions at Visit 3, 52 weeks after the last DL-PDT treatment.

Secondary Endpoints:

- Subject recurrence, defined as the proportion of subjects with recurrence of any (≥ 1) cleared treated AK lesions at Visit 2, 26 weeks after the last DL-PDT treatment;
- Lesion recurrence, defined as the percent recurrence of cleared treated lesions at Visits 2 and 3, 26 and 52 weeks after the last DL-PDT treatment.

The recurrence results will be conveyed in the opposite sense of clearance, i.e., those subjects or lesions that are not CR at Visits 2 and 3 will be deemed to have recurrence.

Safety Assessments:

The following safety assessments are planned according to the schedule of assessments (see [Table 1](#)):

- Adverse events (AEs), Treatment-emergent AEs (TEAEs), and serious AEs (SAEs)

CCI

Statistical Analysis:**Principal Statistical Method**

Populations: The safety population will consist of all enrolled subjects and will be used for all the efficacy and safety analyses.

[figure not shown]
Primary Endpoint: The proportion of subjects with recurrence of any (≥ 1) cleared treated AK lesions at 52 weeks after the last DL-PDT will be summarized using tables of frequency. All subjects in the safety population with missing data will be classified as non-responders regardless of treatment allocation. Summaries by treatment group will be presented for both the imputed data and the observed cases. CCI

Secondary Endpoints: The proportion of subjects with recurrence of any (≥ 1) cleared treated AK lesions at 26 weeks after the last DL-PDT will be summarized using tables of frequency. All subjects in the safety population with missing data will be classified as non-responders regardless of treatment allocation. Summaries by treatment group will be presented for both the imputed data and the observed cases. CCI

The percent recurrence of cleared treated AK lesions at 26 and 52 weeks after the last DL-PDT treatment will be summarized using descriptive statistics. Missing counts of cleared treated AK lesions for subjects in the safety population will be imputed assuming that all baseline AK lesions had recurred regardless of treatment allocation. Summaries by treatment group will be presented for both the imputed data and the observed cases. CCI

Sample Size: There is no formal hypothesis to be tested. The number of 100 completers in the MAL cream arm is deemed sufficient for the descriptive purposes of this study.

Figure 1: Study Schema (Synopsis)

4	TABLE OF CONTENTS	
1	PROTOCOL APPROVAL SIGNATURES	2
2	STUDY PERSONNEL CONTACTS	3
3	SYNOPSIS	4
4	TABLE OF CONTENTS	7
	TABLE OF FIGURES	9
	TABLE OF TABLES	9
5	LIST OF ABBREVIATIONS	10
6	INTRODUCTION	11
6.1	Background & Rationale	11
7	STUDY OBJECTIVES & ENDPOINTS	14
7.1	Primary Objective	14
7.2	Secondary Objective	14
7.3	Primary Endpoint	14
7.4	Secondary Endpoints	14
7.5	Safety Assessments	14
7.6	Other Assessments	14
8	INVESTIGATIONAL PLAN	15
8.1	Overall Study Design and Plan	15
8.1.1	Study Schema	16
8.1.2	Schedule of Assessments	17
8.2	Discussion of Study Design	20
8.2.1	Study Design	20
8.3	Selection of the Study Population	20
8.3.1	Number of Planned Subjects	20
8.3.2	Inclusion Criteria	20
8.3.3	Exclusion Criteria	21
8.3.4	Removal of Subjects From Assessments	21
8.3.5	Method of Continuing already Randomized Subject from Previous study	22
8.3.6	Blinding	22
8.3.7	Prior and Concomitant Therapy	22

1.0	8.4	Duration of Subject Participation	24
	8.4.1	Early Termination Visit	24
	8.5	Unscheduled Visit	24
	9	STUDY ASSESSMENTS.....	25
	9.1	Efficacy Assessments	25
	9.1.1	Lesion Response	25
	9.2	Safety Assessments.....	26
	9.2.1.1	Serious Adverse Events	28
	9.2.1.2	Adverse Events of Special Interest (AESIs).....	29
	9.2.1.3	Procedure for Reporting a Serious Adverse Event.....	29
	9.2.1.4	Procedure for Reporting Pregnancies	30
	9.2.1.5	Unexpected Adverse Reactions	31
	9.2.2	Pregnancy Testing	31
	CCI		32

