7.2 Secondary Objective

The secondary objective of this study is to evaluate the long-term safety of MAL DL-PDT and vehicle cream DL-PDT for 52 weeks after the last DL-PDT for those subjects who achieved Complete Response (CR) of treated AK lesions in study RD.06.SPR.112199.

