8 INVESTIGATIONAL PLAN

8.1 Overall Study Design and Plan

This is a double-blind, vehicle-controlled, multicenter, parallel-group long-term follow-up study to evaluate recurrence of AKs in subjects who completed study RD.06.SPR.112199. Only those subjects who achieved CR of treated AK lesions at the Final Visit of that study will be offered the opportunity to continue to be followed in the current study for 9 months to assess recurrence.

In this study, the results of DL-PDT with MAL 16.8% cream or a vehicle cream will be compared; no intervention occurs in this study.

All subjects will provide written informed consent prior to any study-related procedure.

A total of approximately 130 subjects will continue from the study RD.06.SPR.112199 to be followed for another 40 weeks, which corresponds to 52 weeks after the last DL-PDT. It is anticipated that approximately 111 subjects will continue from the MAL cream arm, and 19 subjects will continue from the vehicle cream arm. Blinding will be maintained through this study.

Subjects will have a combined visit which includes the final visit for the RD.06.SPR.112199 study and the initial visit for this study. Data from the previous study will be pulled into the database for this study. Subjects will return to the study center for another visit at Visit 2 (Week 14, 26 weeks after the last DL-PDT treatment) for efficacy and safety assessments. The investigative site staff will contact the subject via telephone at Week 26 (38 weeks after the last DL-PDT treatment) to determine if the subject is experiencing any treatment-related safety issues.

[figure not shown]
The primary endpoint of this study occurs at Visit 3; Final Visit, Week 40 (52 weeks after the last DL-PDT visit).

The 4 planned interactions are:

Visit 1	Rollover visit from study RD.06.SPR.112199; corresponds to Visit 6 in that study. Only those subjects who achieve CR will be given the opportunity to continue in this long-term follow-up study. All assessments captured are transferred to this study
Visit 2	Week 14 (26 weeks after the last DL-PDT treatment) - Efficacy and safety assessments; CCI
Telephone check in	Week 26 (38 weeks after the last DL-PDT treatment) - Safety assessments
Visit 3	Week 40 Final Visit (52 weeks after the last DL-PDT treatment) - Efficacy and safety assessments; CCI

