7.2. Safety Population

The safety population will consist of all enrolled subjects and will be used for all the efficacy and safety analyses. Screen failures will not be included into the Safety Population.

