9.11.1. Adverse Events Analysis

Treatment-emergent AEs are defined as those AEs occurring after the first administration of study treatment until the last study visit from study RD.06.SPR.112199 and as all AEs in this study RD.06.SPR.115230.

All treatment-emergent AEs will be listed in a by-subject listing which will include both the term reported on the eCRF (verbatim term) and the MedDRA System Organ Class and Preferred Term. Relative start and stop days will be included along with the actual onset and resolution dates.

If relationship is missing the closest relationship, i.e. "Related" will be imputed. If severity is missing the greatest severity, i.e. "Severe", will be imputed.

A summary table of TEAEs will be provided for each of the following for the safety population by treatment group and overall:

- Number and percentage (n, %) of subjects with any TEAE and frequency of TEAEs overall and by System Organ Class and Preferred Term;
- Number and percentage (n, %) of subjects with any TEAE by closest relationship to study drug and frequency of TEAEs by closest relationship to study drug;
- Number and percentage (n, %) of subjects with any TEAE by closest relationship to study procedures and frequency of TEAEs by closest relationship to study procedures;
- Number and percentage (n, %) of subjects with any TEAE related to the study drug and frequency of TEAEs related to the study drug by System Organ Class and Preferred Term;
- Number and percentage (n, %) of subjects with any TEAE related to the study procedures and frequency of TEAEs related to the study procedures by System Organ Class and Preferred Term;
- Number and percentage (n, %) of subjects with any TEAE by greatest severity and frequency of TEAEs by greatest severity overall and by System Organ Class and Preferred Term;
- Number and percentage (n, %) of subjects with any TEAE leading to study discontinuation and frequency of TEAEs leading to study discontinuation.

A summary table of serious TEAEs will be provided for each of the following in the safety population by treatment group and overall:

- Number and percentage (n, %) of subjects with any Serious TEAE and frequency of Serious TEAEs overall and by System Organ Class and Preferred Term;
- Number and percentage (n, %) of subjects with any Serious TEAE by closest relationship to study drug and frequency of Serious TEAEs by closest relationship to study drug;

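### SAP 9.11.1 pools adverse events from the parent study's first DL-PDT onwards in enrolled subjects only, so exclusion criterion 1 can bias malignancy and life-threatening event rates low unless the tables are split at Visit 1

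*Protocol*

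**What the plan says.** - **Objective.** Protocol 7.2 and SAP 3.2 set out to "evaluate the long-term safety of MAL DL-PDT and vehicle cream DL-PDT for 52 weeks after the last DL-PDT" in subjects who were complete responders in RD.06.SPR.112199. Neither limits this to responders still free of serious disease at rollover.
- **Entry rule.** Exclusion criterion 1 (Protocol synopsis and 8.3.3) covers "Subjects, who develop or experience a condition that may compromise subject safety or compliance, interfere with evaluation or preclude completion of the study" and adds: "In particular, these conditions include, but are not limited to malignancy or other life threatening diseases".
- **Timing.** Eligibility is settled at Visit 1, which Protocol 8.1 describes as "Rollover visit from study RD.06.SPR.112199; corresponds to Visit 6 in that study".
- **Population.** SAP 7.2 states "The safety population will consist of all enrolled subjects and will be used for all the efficacy and safety analyses" and then "Screen failures will not be included into the Safety Population". SAP 9.11 uses this population for every safety analysis.
- **Event window.** SAP 9.11.1 states "Treatment-emergent AEs are defined as those AEs occurring after the first administration of study treatment until the last study visit from study RD.06.SPR.112199", and adds every adverse event of the present study.
- **Tables.** Protocol 10.1.4.1 calls for treatment-emergent events to be tabulated separately by study phase. The list in SAP 9.11.1 gives tables by treatment group and overall and does not state that split.
- **Excluded subjects.** They appear in the disposition summary (SAP 9.2.1) as screen failures with reasons, and nowhere in the safety tables.

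**The concern.** The event window opens about 14 weeks before the population is defined, and the rule that defines the population can depend on events inside that window. A complete responder who develops a malignancy between the first DL-PDT and rollover may be refused entry because of it. The pooled table then includes the lead-in for everyone else, with some of the events that matter most selected out of it.

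The Protocol background (6.1) describes actinic keratosis as the earliest recognizable form of squamous cell carcinoma, so malignancy is an outcome readers will look for. An interim analysis of all available data is planned at the time of regulatory submission (Protocol 10.1.5, SAP 9.9), so these tables may be read in that setting. A reader would take them as 52-week safety in complete responders. They describe complete responders who had already passed a health screen part-way through the window.

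**Working it through.** **Consistency of the plan's own figures**

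Protocol 8.2.1 gives 380 MAL and 190 vehicle subjects with assumed complete response of 45% and 15%.

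- MAL: 380 × 0.45 = 171. Vehicle: 190 × 0.15 = 28.5. Total 199.5 complete responders.
- Expected enrolment is 111 + 19 = 130, and 130 / 199.5 = 65%.
- An assumed 65% rollover gives 171 × 0.65 = 111.2 and 28.5 × 0.65 = 18.5. An assumed 10% dropout gives 100 / 0.90 = 111.1 for 100 MAL completers.

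The enrolment figures are coherent. The rollover and dropout rates are not in the visible text, so they are back-solved here. What matters is that 130 is expected enrolment, not the number of complete responders, which is about 200.

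**Share of the window affected**

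- Clock of SAP 9.11.1 (from first DL-PDT): entry at week 14, end at week 54, so 14 / 54 = 26%.
- Clock of the objective (from last DL-PDT): 12 / 52 = 23%.
- Weather delays, session spacing and the Visit 6 window can lengthen the lead-in. With 40 weeks kept after entry, 16 weeks gives 16 / 56 = 29% and 20 weeks gives 20 / 60 = 33%.

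**Illustrative size**

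The documents give no event rate. Assume a constant hazard h per year, a 14-week lead-in, 40 weeks of follow-up, and exclusion of every subject with such an event.

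- Incidence shown in the pooled table: 1 − exp(−h × 40/52)
- Incidence over the whole window: 1 − exp(−h × 54/52)
- Lead-in probability: p = 1 − exp(−h × 14/52)
- Subjects kept out per 130 enrolled: 130 × p / (1 − p)

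| Assumed h per year | Shown | Whole window | Ratio | Kept out per 130 | MAL (111) | Vehicle (19) |
|---|---|---|---|---|---|---|
| 1% | 0.77% | 1.03% | 0.74 | 0.35 | 0.30 | 0.05 |
| 2% | 1.53% | 2.06% | 0.74 | 0.70 | 0.60 | 0.10 |
| 5% | 3.77% | 5.06% | 0.75 | 1.76 | 1.50 | 0.26 |

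If sites exclude only half of such subjects, the understatement is roughly 0.5 × 26% = 13%.

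The expected loss is small, but so are the counts. One omitted subject is the difference between 0/111 and 1/112 (0.9%) in the MAL arm, or between 0/19 and 1/20 (5%) in the vehicle arm.

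**The case against.** **The protocol already has the safeguard.** Protocol 10.1.4.1 tabulates by study phase, the SAP exists to carry out Protocol section 10, the table shells are in a separate document that is not available here, and the by-subject listing carries relative start days. This largely stands. It reduces the point to an omission in SAP 9.11.1, which should state the split and not leave it to the shells. A phase split alone also does not show who was kept out.

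**The criterion has a purpose.** Since "Neither investigational product nor intervention will be part of this study", a reader might infer that criterion 1 is unjustified and should be cut back. The documents do not support that. Protocol Table 2 bars several surgical, radiation, photodynamic and immunosuppressive treatments in the treatment area because they may interfere with lesion assessment, and some of these could be used for a malignancy. Excluding such subjects is defensible in a study whose primary endpoint is recurrence.

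**Starting the count at Visit 1 for these events would be worse.** The criterion leaves room for judgment, so a subject with a resolved skin cancer could be enrolled. Discarding earlier onsets would delete an observed malignancy. This stands, and the fix avoids it.

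**Not everything missing is due to criterion 1.** About 199.5 − 130 = 70 complete responders are expected not to enrol in any case, and some very ill subjects would never reach rollover. Lead-in events are also collected in the parent study, whose reporting is not available here. Both points limit the claim. Neither changes how this study's pooled tables read.

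**Conclusion.** The point holds in a limited form. SAP 9.11.1 lists tables over a window that includes the lead-in, for a population selected at the end of it, and criterion 1 can remove subjects because of lead-in events. Pooled incidences of malignancy and life-threatening disease can therefore be biased low relative to the stated objective. Under a constant hazard and strict exclusion the tables would show about 74% to 75% of the whole-window incidence, with 0.35 to 1.8 subjects kept out per 130 enrolled at assumed rates of 1% to 5% per year. The true size is unknown.

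Three stronger readings are tempting and not supported:

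- That all treatment-emergent and serious event rates are understated. Only malignancy, life-threatening or similarly disqualifying events with onset before Visit 1, and actually used to refuse entry, are affected. Later events in enrolled subjects are counted.
- That the comparison favours MAL. The criterion applies to both arms with investigators blinded, and no between-arm bias is shown.
- That the early events are lost altogether. They are absent from this study's safety tables; what the parent study reports cannot be judged from these documents.

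This is worth correcting because the outcome is important and the correction is cheap.

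**What to change.** Leave the eligibility criteria unchanged and amend SAP 9.11.1:

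1. Present the treatment-emergent and serious treatment-emergent event tables separately for onset before Visit 1 and onset on or after Visit 1, in line with Protocol 10.1.4.1. Keep every observed event in one table or the other.
2. Label both sets as conditional on enrolment in the follow-up study.
3. Beside them, show by arm the number of complete responders screened out under criterion 1 and the condition concerned, using the screen-failure reasons already planned in SAP 9.2.1. Add a note that complete responders who never consented may not appear in that count.

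The cost is some SAP wording, a little more table work, one small additional display and sparser counts within each phase. No protocol amendment is needed, and the change works even if enrolment has closed.

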5 LIST OF ABBREVIATIONS

AE	Adverse Event
AK	Actinic keratosis
BCC	Basal cell carcinoma
BL	Baseline
CI	Confidence interval
CR	Complete response
CRO	Contract research organization
CS	Clinically significant
c-PDT	Conventional PDT
DL	Daylight
eCRF	Electronic Case Report Form
EDC	Electronic data capture
ET	Early termination
FDA	Food and Drug Administration
FST	Fitzpatrick Skin Type
GCP	Good Clinical Practice
HIPAA	Health Insurance Portability and Accountability Act
IB	Investigator's Brochure
IC	Informed Consent
ICF	Informed consent form
ICH	International Council for Harmonisation of Technical Requirements for Pharmaceuticals for Human Use
IEC	Independent Ethics Committee
IRB	Institutional Review Board
LTFU	Long-term follow-up
MAL	Methyl aminolevinulate hydrochloride
MedDRA	Medical Dictionary for Regulatory Activities
NDA	New drug application
PDT	Photodynamic Therapy
PpIX	Protoporphyrin IX
SAE	Serious adverse event
SAP	Statistical analysis plan
SCC	Squamous cell carcinoma
SIN	Subject identification number
SOC	System Organ Class
SUSAR	Suspected unexpected serious adverse reaction
TA	Treatment area
TEAE	Treatment-emergent adverse event
TMF	Trial Master File
UPT	Urine pregnancy test
US	United States
UV	Ultraviolet

